3.7.4.1 Physical Examinations

Subjects with abnormalities in each body system examined will be presented for each scheduled evaluation in data listings.

3.7.4.2 Vital Signs

Vital sign parameters (systolic and diastolic blood pressure, pulse rate, respiration rate, and temperature) will be summarized with descriptive statistics for each scheduled evaluation by

treatment group and MEDI5884 overall. Change from baseline to each post baseline evaluation will also be summarized. In addition, changes from pre-dose to 1 hour post-dose will be summarized for each dosing visit.

3.7.4.3 Electrocardiogram

The following ECG parameters will be summarized: Heart rate, RR, PR, QRS and QT intervals as well as derived parameters QT corrected interval parameters, QTcB (Bazett's formula) and QTcF (Fridericia's formula). The results at each visit: Baseline (average of the 3 triplicate ECG averages taken on [REDACTED] and at each post-baseline visit (average of ECG triplicate) will be summarized as well as the change from baseline. In addition, the number of subjects having the following notable ECG interval values will be summarized.

- Maximum QTcF and QTcB intervals > 450 ms, > 480 ms, > 500 ms
- Maximum uncorrected QT intervals > 500 ms
- Maximum changes from baseline in QTcF and QTcB > 30 , > 60 and > 90 ms

The percent of subjects with an abnormal ECG evaluation and specific ECG abnormalities observed at each visit will be summarized by treatment group and MEDI5884 overall.

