2 OBJECTIVES AND ENDPOINTS

2.1 Primary Objective and Associated Endpoint

Table 2.1-1 Primary Objective and Associated Endpoints

Type	Objective	Endpoint
Safety	Evaluate the safety and tolerability of repeated [REDACTED] dosing with MEDI5884 in subjects with stable CHD	
• Occurrence of TEAEs and TESAEs and clinically important changes in ECGs, vital signs, clinical laboratory evaluations and physical examination up to end of study ([REDACTED])

CHD = coronary heart disease; ECG = electrocardiogram; TEAE = treatment-emergent adverse events; TESAE = treatment-emergent serious adverse events

[figure not shown]

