4.1.3 Exclusion Criteria

Any of the following would exclude the subject from participation in the study:

1. Unstable cardiovascular conditions, including acute coronary syndrome, stroke or transient ischemia attack, critical limb ischemia, arterial revascularization, life-threatening arrhythmias, or heart failure hospitalization within [REDACTED] of Screening
2. Any planned arterial revascularization (coronary, peripheral or carotid)
3. New York Heart Association Class III or IV congestive heart failure or treatment with advanced therapies (cardiac transplant, ventricular assist device, cardiac resynchronization therapy, and/or chronic intravenous ionotropic support)
4. Severe valvular heart disease
5. Fasting laboratory values at Screening for any of the following:
 - a. Triglycerides >500 mg/dL
 - b. LDL-C >100 mg/dL (by direct measure)
6. Clinically significant BP abnormalities at Screening after 10 minutes supine rest:
 - a. Systolic BP <90 or >160 mmHg
 - b. Diastolic BP >100 mmHg

Note: BP may be retested one time at the discretion of the investigator.
7. ECG results from the central lab report at Screening, demonstrating:
 - a. Prolonged QTcF >460 milliseconds based on reported mean of any ECG, or
 - b. QRS >160 milliseconds based on reported mean of any ECG
8. Family history of long QT, or any clinically significant ECG finding as judged by the investigator (at [REDACTED]) that may interfere with the interpretation of serial ECG and QT interval changes
9. Current or previous use of lipid-lowering medications within [REDACTED] prior to Screening, except for statins and/or <100-mg/day niacin, and/or 10-mg/day ezetimibe, and/or <2-g/day fish oil
10. History of any of the following:
 - a. Documented genetic disorder of cholesterol metabolism
 - b. Chronic kidney disease stage 4-5, defined by estimated glomerular filtration rate <30 mL/min/1.73 m² by the modification of diet in renal disease equation, or end stage renal disease treated with kidney transplant or renal replacement therapy
 - c. History of clinically overt chronic liver disease or biochemical evidence of liver disease (eg, aspartate transaminase [AST] or alanine transaminase [ALT] >1.5 × upper limit of normal [ULN] and/or total bilirubin [TBL] >ULN [unless due to Gilbert's syndrome])
 - d. Poorly controlled endocrine disorder including Type 1 or Type 2 diabetes mellitus with glycated hemoglobin >10% as assessed at Screening

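### The SAP's absolute QTc counts, chiefly the row above 450 ms, set no condition on baseline, so subjects already prolonged at entry are counted together with newly prolonged ones

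*SAP*

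**What the plan says.** SAP 3.7.4.3 states that "the number of subjects having the following notable ECG interval values will be summarized". The list that follows contains "Maximum QTcF and QTcB intervals > 450 ms", with further limits at 480 and 500 ms, an uncorrected QT count above 500 ms, and "Maximum changes from baseline in QTcF and QTcB > 30 , > 60 and > 90 ms". The absolute-value items carry no baseline condition and no new-onset rule, and they do not restrict the maximum to post-baseline visits.

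The section defines baseline well: "Baseline (average of the 3 triplicate ECG averages taken on" a day that is blacked out. It also says that the results at baseline and at each later visit "will be summarized as well as the change from baseline".

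On entry, Protocol 4.1.3 item 7a excludes "Prolonged QTcF >460 milliseconds based on reported mean of any ECG", assessed at Screening. Item 7b concerns QRS. Neither item sets a QTcB limit, although Protocol 4.3.2.4 derives QTcB and the SAP counts it.

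The primary endpoint in Protocol 2.1 includes "clinically important changes in ECGs".

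**The concern.** A count of subjects above 450 ms is naturally read as a count of subjects who became prolonged on treatment. As written, it mixes them with subjects who were already above 450 ms before the first dose. The SAP avoids this mixing in neighbouring sections: laboratory results are tabulated as shifts from the baseline category (3.7.4), and adverse events count as treatment-emergent only if they start after the first dose (3.7.1). The absolute QTc rows have no such safeguard.

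Groups have 20 subjects and safety differences are judged by eye for medical relevance. One or two extra pre-existing cases in a group could make a dose look worse than placebo, or hide a real shift if they fall in the placebo group. The maximum over several visits means that almost every subject who starts above 450 ms will be counted.

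**Working it through.** **1. Thresholds.** These come from the documents.
- QTcF: 460 − 450 = 10 ms. Subjects admitted in this band can be counted as above 450 ms with no change on treatment.
- The screening limit lies 480 − 460 = 20 ms and 500 − 460 = 40 ms below the other two thresholds, so for QTcF the overlap is essentially confined to the 450 ms row. The limit applies at Screening, so it does not strictly bound the baseline-visit value.
- QTcB: no entry limit is listed, so overlap is possible at all three thresholds.

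**2. Do the change rows cover the gap?** Only partly. A subject going from 440 to 465 ms rises by 25 ms. This is a new value above 450 ms, but it misses the change count above 30 ms. A subject constant at 455 ms is in the absolute row and in no change row. Neither set of rows shows who newly crossed a limit.

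**3. Size, for illustration.** The plan states no figure to reproduce, and every distributional input here is an assumption. Simulated without drug effect: true QTcF normal with mean 415, 425 or 435 ms and between-subject SD 18; independent visit-to-visit SD 8; entry only if screening QTcF ≤460 ms; baseline as the mean of three readings (SD 8/√3); five post-baseline visits.

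| Assumed mean QTcF (ms) | 415 | 425 | 435 |
|---|---|---|---|
| (a) Baseline >450 ms | 2.1% | 5.9% | 13.0% |
| (b) Maximum >450 ms, as written | 7.5% | 17.1% | 31.1% |
| (c) Share of (b) with baseline >450 ms | 26% | 33% | 40% |
| (d) New onset, (b) × (1 − c) | 5.6% | 11.5% | 18.6% |
| Expected count per 20 as written, 20 × (b) | 1.5 | 3.4 | 6.2 |
| Expected new-onset count per 20, 20 × (d) | 1.1 | 2.3 | 3.7 |
| At least one of 20 with baseline >450 ms, 1 − (1 − a)^20 | 35% | 70% | 94% |

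The proportion of subjects above 450 ms at baseline who end up in the count is (c) × (b) / (a), about 93-96%.

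**4. Wider inputs.** Mean 410-430 ms, between-subject SD 15-20, visit SD 6-10 and six post-baseline visits give:
- baseline above 450 ms in 0.4-10% of subjects;
- a pre-existing share of the count of 10-45%;
- a chance of at least one such subject in a group of 20 of 8-88%;
- a maximum above 480 ms in under 1% of subjects.

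**5. What a baseline condition would achieve.** The SD of the chance difference in counts between two groups of 20 is √(2 × 20 × p(1 − p)).
- With p = (b): 1.7, 2.4 and 2.9.
- With p = (d): 1.5, 2.0 and 2.5.

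The reduction is about 13-16%. Most no-effect counts, 60-74% (that is, 1 − c), come from subjects just below 450 ms whose maximum crosses it, and these remain.

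**The case against.** A reader might infer that the ECG table does not measure change on treatment at all. The documents do not support that. The same list counts maximum increases above 30, 60 and 90 ms, and change from baseline is summarized at each visit. Under the inputs of step 3, the count above 30 ms picks up only about 0.3% of subjects when there is no effect.

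A reader might also infer that the primary endpoint is compromised. SAP 3.7 measures the primary safety endpoints by the incidence of TEAEs and TESAEs, asks investigators to record clinically important ECG changes as adverse events, and makes no formal safety comparisons. New onset is already built into that measure, and the interval counts are supplementary.

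Further points carry some weight:
- Placebo subjects enter under the same limit, so pre-existing cases balance on average, though not reliably in groups of 20.
- Exclusion 8 and the predose ECG check in Protocol 4.3.2.4 may remove some subjects, but both rest on the investigator's judgment and set no QTc value.
- Listings would show baseline values.
- Table layouts are left to a statistical programming plan that is not among the documents. A baseline split there cannot be ruled out, but the SAP does not require one.
- Restricting on baseline leaves most of the chance variation between groups in place (step 5).

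These arguments limit the scope and importance of the point. They do not change the fact that the absolute rows, as specified, cannot separate pre-existing from new prolongation.

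**Conclusion.** The point holds for the absolute-value rows only: chiefly QTcF above 450 ms, and possibly any QTcB threshold because no QTcB entry limit is listed. That follows from the two documents without any assumption. The size does not: a pre-existing share of 26-40% of the QTcF count above 450 ms (10-45% over wider inputs) rests on assumed QTcF means and SDs, independent visits and no drug effect. No figure was derived for QTcB or for uncorrected QT.

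This is a minor, inexpensive improvement to a descriptive safety table. It has no bearing on any test, error rate or sample size. It should not be presented as a failure to assess ECG change, nor as a way to remove chance imbalance from the row.

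**What to change.** In SAP 3.7.4.3:
- State that the maximum is the maximum post-baseline value.
- For QTcF and QTcB, keep the existing count and add beside it either (i) a new-onset count for each limit (baseline at or below the limit, maximum post-baseline value above it, with subjects at or below the limit at baseline as denominator), or (ii) a shift table of baseline category by maximum post-baseline category, in line with the laboratory shift tables in 3.7.4.
- List the subjects already above a limit at baseline.

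The baseline is already defined in the section, so no new data are needed. The cost is SAP wording, one programming condition, one extra row or table, and slightly smaller denominators in the new-onset row above 450 ms. The change does not remove chance counts that arise from taking a maximum over several visits, so the new row should still be read alongside the change-from-baseline counts.

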4.1.2 Inclusion Criteria

Subjects must meet all of the following criteria:

1. Male or female adult aged 45 through 80 years, inclusive, at the time of Screening
2. Written informed consent and any locally required authorization (eg, data privacy) obtained from the subject prior to performing any protocol-related procedures, including screening evaluations
3. Written informed consent if participating in the optional future use research or genetic research. Declining to participate in this part of the study will not result in penalty or loss of benefit to the subject
4. Ability to meet all eligibility requirements for randomization within up to [REDACTED] after signing the informed consent form
5. Ability and willingness to adhere to visit/protocol schedule and complete the follow-up period
6. Diagnosis of stable CHD documented prior to Screening defined as a history of at least one of the following:
 - a. prior myocardial infarction,
 - b. coronary revascularization,
 - c. coronary atherosclerosis diagnosed >3 months prior to Screening, based on invasive or non-invasive imaging,
 - d. abnormal stress testing diagnostic of CHD
7. Currently receiving any high-intensity statin (≥ 40 -mg atorvastatin or ≥ 20 -mg rosuvastatin for non-Asian subjects; ≥ 10 -mg rosuvastatin for Asian subjects) at a stable dose for ≥ 30 days prior to Screening and intending to remain at a stable dose throughout the study duration.
8. Females must not be of childbearing potential and must not be lactating (see Section 10.2 for definition of females of childbearing potential)
9. Nonsterilized male subjects who are sexually active with a female partner of childbearing potential must use a male condom with spermicide from [REDACTED] through the end of their participation in the study. It is strongly recommended for the female partner of a male subject to also use a highly effective method of contraception throughout this period, as described in Section 10.2.

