3.7.4 Clinical Laboratory Evaluation

The hematology and serum chemistry parameters as well as their changes from baseline will be summarized with descriptive statistics by treatment group at each of the scheduled visits. In addition, hematology and serum chemistry values will also be classified as low, normal, or high with respect to the laboratory reference range for the parameter. The shift from baseline category to each post-baseline visit category for each parameter will be summarized at each post-baseline visit by treatment group as well as for MEDI5884 overall.

The urinalysis categorical results will be classified as normal or abnormal with respect to the laboratory reference range for the parameter. The shift from baseline category to the post-baseline category will be summarized by treatment group and MEDI5884 overall at each post-baseline visit.

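### The qualitative ECG summary gives prevalence at each visit and does not count abnormalities that are new since baseline

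*SAP*

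**What the plan says.** Protocol 2.1 includes in the primary endpoint "clinically important changes in ECGs, vital signs, clinical laboratory evaluations and physical examination up to end of study".

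SAP 3.7.4.3 treats the ECG in two ways. Heart rate and the RR, PR, QRS, QT and QTc intervals are summarized as values and as changes from baseline, with threshold counts that include "Maximum changes from baseline in QTcF and QTcB". The qualitative reading, meaning the normal/abnormal evaluation and the named abnormalities, has one sentence: "The percent of subjects with an abnormal ECG evaluation and specific ECG abnormalities observed at each visit will be summarized", by treatment group and for MEDI5884 overall. That sentence makes no reference to baseline, and the section does not define a new or treatment-emergent ECG abnormality. Protocol 4.8.3.2 adds only that ECG parameters are summarized descriptively.

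SAP 3.7.4 handles laboratory categories differently. For hematology and chemistry: "The shift from baseline category to each post-baseline visit category for each parameter will be summarized at each post-baseline visit by treatment group". For urinalysis, which is classed as normal or abnormal: "The shift from baseline category to the post-baseline category will be summarized by treatment group and MEDI5884 overall at each post-baseline visit".

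Protocol 4.3.2.4 has a paper ECG read as normal or abnormal before dosing and on study days, so a within-subject comparison can be made.

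**The concern.** The endpoint asks about change, and a percentage at each visit describes state. All subjects have coronary heart disease, and "prior myocardial infarction" is one of the qualifying histories in Protocol 4.1.2, so some are likely to enter with an abnormal tracing. A per-visit percentage then combines abnormalities that predate treatment with those that arise on it, and a new abnormality in one subject offsets a resolved one in another. Nor do the percentages accumulate across visits: different subjects, each abnormal at one visit only, never appear together in any column.

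At stake is the readability of one safety table. New rhythm, conduction or ischemic findings matter in this population, and the qualitative table is where a reader would look for them by arm. The SAP gives no reason for treating the ECG reading differently from urinalysis.

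**Working it through.** The plan states no figure on this point, so there is none to reproduce.

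**1. What per-visit counts reveal about new cases.** Let n be the arm size, B the number abnormal at baseline, P the number abnormal at a later visit, N the newly abnormal and R the resolved. Then P = B − R + N. From B and P alone, N lies between max(0, P − B) and min(P, n − B). No effect size is assumed. The arm size of 20 comes from the treatment table in Protocol 3.1.2. The values of B and P are illustrative, and the same subjects are assumed to be read at both times.

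| n | B | P | Range for N |
|---|---|---|---|
| 20 | 6 | 6 | 0 to 6 |
| 20 | 8 | 8 | 0 to 8 |
| 20 | 10 | 10 | 0 to 10 |
| 20 | 12 | 14 | 2 to 8 |
| 100 (five MEDI5884 arms) | 50 | 50 | 0 to 50 |

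The net rise P − B is therefore only a lower bound on N. For a specific abnormality, 0/20 then 2/20 means exactly 2 new cases, whereas 3/20 then 3/20 means 0 to 3. A shift table gives N itself.

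**2. Illustration of what this costs.** Every rate here is an assumption: baseline abnormality b of 30% to 60%; among subjects normal at baseline, 25% newly abnormal on MEDI5884 and 5% on placebo; a fraction r of baseline abnormalities resolving, equal in all arms.

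The expected difference in percent abnormal is (1 − b) × (0.25 − 0.05), which is 14, 12, 10 and 8 points for b = 30%, 40%, 50% and 60%. The excess among those at risk is 20 points.

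Signal-to-noise (difference divided by its standard error), 100 on MEDI5884 against 20 on placebo:

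- *Post-baseline prevalence alone, r = 20%.* At b = 30% the percentages are 41.5 and 27.5: 0.14/√(0.415×0.585/100 + 0.275×0.725/20) = 1.26. At b = 60% they are 58 and 50: 0.08/√(0.58×0.42/100 + 0.50×0.50/20) = 0.65.
- *Change in percent abnormal from baseline.* With q the rate of new abnormality, the variance per subject is (1−b)q + br − [(1−b)q − br]². At r = 20%, b = 30%: 0.14/√(0.2218/100 + 0.0944/20) = 1.7. At r = 20%, b = 60%: 0.08/√(0.2196/100 + 0.1300/20) = 0.86. With r = 0 the same formula gives 2.5 and 1.8.
- *New abnormalities among those normal at baseline.* With 70 and 14 at risk: 0.20/√(0.25×0.75/70 + 0.05×0.95/14) = 2.6. With 40 and 8 at risk: 0.20/√(0.25×0.75/40 + 0.05×0.95/8) = 1.9.

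If old abnormalities persist and the table shows a baseline column, almost nothing is lost (2.5 to 1.8 against 2.6 to 1.9). The loss comes mainly from abnormalities that come and go.

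**The case against.** The strongest reply is that the endpoint component is already covered. SAP 3.7 has investigators record clinically important ECG changes as adverse events. SAP 3.7.1 counts those with onset after first dose by treatment group and MEDI5884 overall. Descriptive ECG readings are listed, and changes from baseline in PR and QRS would pick up some conduction effects. This stands, and it limits the gap. But adverse event entry depends on investigator judgment and listings give no count by arm. The SAP also plans laboratory shift tables although important laboratory changes are likewise recorded as adverse events.

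Baseline abnormality is also partly screened out. Protocol 4.1.3 excludes QTcF above 460 ms, QRS above 160 ms, and clinically significant findings that may interfere with serial ECG interpretation. Protocol 4.3.2.4 bars dosing when a predose ECG shows a clinically significant abnormality. These rules remove some abnormal tracings, not all, and how many remain is unknown.

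A reader might infer that the planned table cannot show new abnormalities at all. The documents do not support that. Specific abnormalities are tabulated, there is a concurrent placebo arm, and SAP 3.7.4.3 describes its numeric results at baseline and each later visit, so a baseline column is a natural reading here too, though not an explicit one. A net rise, or a finding absent from an arm at baseline, would be visible.

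Finally, SAP 1 defers table templates to a separate programming plan, which may contain a shift layout. The SAP text names none.

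**Conclusion.** The gap is real and moderate. The SAP summarizes the qualitative ECG as prevalence at each visit, without a baseline reference, for a component of the primary endpoint that concerns change. Such a table bounds the number of new cases and does not give it; in an arm of 20 with an unchanged count of 10, the bound is 0 to 10. That result is arithmetic and needs no assumed rates.

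The signal-to-noise figures do depend on assumed rates. A reader might take them as the trial's actual loss, but the documents give no baseline abnormality, onset or resolution rate, so they show direction only. Nor does it follow that an ECG harm would go unseen, given the adverse event tables, listings and interval changes. SAP 3.7 plans no formal safety comparisons, so alpha, power and sample size are unaffected. This is a cheap improvement.

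**What to change.** In SAP 3.7.4.3, add two summaries by treatment group and for MEDI5884 overall:

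1. A shift table of the overall evaluation (normal/abnormal) from predose baseline to each post-baseline visit and to the worst post-baseline evaluation.
2. For each specific abnormality, the number of subjects who have it at any post-baseline visit among those without it at baseline, with that denominator shown.

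State which predose reading is the qualitative baseline. The average of three triplicates used for intervals cannot be applied to a category; the general rule in SAP 3.1, the last valid assessment before first dose, can be. The per-visit percentages can stay.

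The cost is SAP wording and the programming of two descriptive tables from evaluations already collected. No new data or assessments are needed.

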3.8 Immunogenicity

The immunogenicity analyses will be based on the ADA evaluable population. ADA incidence rate and titer will be tabulated for each treatment group. Samples confirmed positive for ADA will be tested and analyzed for nAb titer and summarized similarly. For overall post-baseline summary, persistent positive is defined as positive at ≥ 2 post-baseline assessments (with ≥ 16 weeks between first and last positive) or positive at last post-baseline assessment; transient positive is defined as negative at last post-baseline assessment and positive at only one post-baseline assessment or at ≥ 2 post-baseline assessments (with < 16 weeks between first and last positive).

